# Exploratory Objectives

- To assess the anti-tumor immune response
  - Quantification of CD8 T cell, CD4 T cell, Treg, CD8/Treg, CD4/Treg, PMN-MDSC and other immune cell populations in a subset of patients (at least 10 per arm) with tumor specimens before and after treatment by immunohistochemistry (IHC). Immune cell density and proximity will also be assessed using polychromatic immunofluorescence.
  - Quantification a range of immunologic markers in a subset of patients (at least 10 per arm) with tumor specimens before and after treatment.
  - Quantification of tumor cell apoptosis by TUNEL and caspase-3 staining.
  - Quantification of circulating IL-8 and other cytokines before and after treatment and correlation with response to therapy.
  - Quantification of circulating PMN-MDSCs and other immune cell populations before and after treatment and correlation with response to therapy.

- Assess whether treatment can induce an increased IgG response to tumor antigens (epitope spreading) by comparing pre- and post-treatment sera.
- Assess the DNA or RNA-related molecular characteristics of tumor specimens and correlate with response to treatment (if adequate tissue available).

# **INVESTIGATIONAL AGENTS**

## Nivolumab

### Pharmaceutical and Therapeutic Background

Nivolumab (also referred to as BMS-936558, MDX1106, or ONO-4538) is a human monoclonal antibody (HuMAb; immunoglobulin G4 [IgG4]-S228P) that targets the programmed death-1 (PD-1) cluster of differentiation 279 (CD279) cell surface membrane receptor. PD-1 is a negative regulatory molecule expressed by activated T and B lymphocytes.1 Binding of PD-1 to its ligands, programmed death-ligands 1 (PD-L1) and 2 (PD-L2), results in the down-regulation of lymphocyte activation. Inhibition of the interaction between PD-1 and its ligands promotes immune responses and antigen-specific T-cell responses to both foreign antigens as well as self-antigens. Nivolumab is expressed in Chinese hamster ovary (CHO) cells and is produced using standard mammalian cell cultivation and chromatographic purification technologies. The clinical study product is a sterile solution for parenteral administration.

OPDIVO (nivolumab) is approved for the treatment of several types of cancer in multiple regions including the United States (US, Dec-2014), the European Union (EU, Jun-2015), and Japan (Jul-2014). Nivolumab is also now FDA-approved for treatment at a dose of 480mg every 4 weeks as a 30 minute infusion (US, Mar-2018). Nivolumab is also being investigated in various other types of cancer as monotherapy or in combination with other therapies, and as single-dose monotherapy for the treatment of sepsis.

# BMS-986253

# Pharmaceutical and Therapeutic Background

BMS-986253 (also known as Humax-IL8 and formerly referred to as Humax-Inflam) is a fully human immunoglobulin subclass G1 kappa monoclonal antibody (mAb) directed against IL-8, also known as CXCL8. IL-8 is a well-described proinflammatory cytokine that has immunosuppressive and protumoral effects in the tumor microenvironment. BMS-986253 potently binds free IL-8. Disruption of the IL-8:CXCR1/2 signaling axis may inhibit recruitment of immunosuppressive myeloid-derived suppressor cells (MDSCs) to the tumor microenvironment, reduce cancer stem cell (CSC) renewal, reverse epithelial mesenchymal transition (EMT), and inhibit angiogenesis, all of which are important mechanisms for cancer-induced immunosuppression, tumor recurrence, and metastasis.

The drug was initially investigated for the treatment of inflammatory skin diseases under the name Humax-Inflam. HuMax-Inflam was in a Phase 1/2 dose-escalation, safety, and efficacy trial in patients with palmoplantar pustulosis (PPP). The antibody demonstrated a tolerable profile and sign of activity based on a reduced inflammation index at doses up to 8 mg/kg weekly.

Subsequently, the product is now being developed for the treatment of cancer under the product code BMS-986253. The clinical development strategy for BMS-986253 as an anticancer agent will be in combination with other therapeutic approaches such as immune checkpoint inhibitors.

The transition from hybridoma-derived to Chinese hamster ovary (CHO) cell-derived BMS-986253 was accomplished by the cloning and expression of the heavy and light chains of the antibody cDNAs in CHO cells to produce BMS-986253. A comparability exercise between CHO cell-derived material and hybridoma material has not revealed any significant differences in antigen-binding fragment (Fab) to IL-8 and other critical quality attributes, but has demonstrated a more complete processing and decreased heterogeneity in isoelectric point with the CHO cellderived BMS-986253. Based on molecular characterization, the main difference between the hybridoma-derived and CHO cell-derived materials is glycosylation patterns. The transition from hybridoma-derived to Chinese hamster ovary (CHO) cell-derived BMS-986253 was accomplished by the cloning and expression of the heavy and light chains of the antibody cDNAs in CHO cells to produce BMS-986253. A comparability exercise between CHO cell-derived material and hybridoma material has not revealed any significant differences in antigen-binding fragment (Fab) to IL-8 and other critical quality attributes, but has demonstrated a more complete processing and decreased heterogeneity in isoelectric point with the CHO cell-derived BMS-986253. Based on molecular characterization, the main difference between the hybridoma-derived and CHO cellderived materials is glycosylation patterns.

BMS-986253 was tested as monotherapy in 15 participants with advanced solid tumors (Study CA027-001) and demonstrated a tolerable profile at doses up to 32 mg/kg. Of these 15 participants, 11 had a best overall response of stable disease (SD) and 4 had a best overall response of progressive disease. In an ongoing Phase 1/2a study of BMS-986253 in combination with nivolumab in advanced cancers, safety data from the first 8 participants suggest that the drug combination is well tolerated.

The clinical development strategy for BMS-986253 as an anti-cancer agent will be in combination with other therapeutic approaches such as immune checkpoint inhibitors. It is hypothesized that inhibition of MDSC and neutrophil tumor infiltration, reduction of CSC renewal, and reversal of cancer cell EMT driven by anti-IL-8 disruption of the IL-8:CXCR1/2 signaling axis will further sensitize IL-8 producing tumors to other therapeutic approaches such as immune checkpoint blockade.

# **STUDY DESIGN**

# General Design

This is a multi-center, two-arm, open-label, phase 1b/2 study evaluating the anti-tumor effect of either Nivolumab alone or Nivolumab plus BMS-986253 with androgen deprivation therapy using Degarelix in men with hormone-sensitive prostate cancer and a rising PSA. Patients will be recruited from outpatient clinics at participating sites and randomized to either Nivolumab alone (Arm A) or Nivolumab plus BMS-986253 (Arm B).

**Study Interventions:** Eligible patients in Arm A will receive Nivolumab every 4 weeks for 2 doses and then Nivolumab + Degarelix every 4 weeks x 4 doses. Eligible patients in Arm B will receive Nivolumab every 4 weeks x2 doses + BMS-986253 every 2 weeks x 4 doses and then

Nivolumab every 4 weeks x 4 doses + BMS-986253 every 2 weeks x 8 doses + Degarelix every 4 weeks x 4 doses.

Schedule of Evaluations: During treatment patients will have safety assessments including routine bloodwork and physical examinations at each visit. (See Section 12 for detailed study evaluations and the study schedule). Safety evaluations will also occur until 100 days after the last treatment doses.

The primary endpoint will be evaluated by assessing the PSA 10 months after start of therapy. PSA and serum testosterone will be checked monthly during treatment (+/- 3 days), the end of treatment visit (+/- 1 week), every 2 months (+/- 1 week) or until progression of disease during year 1 of follow up and every 3 months (+/- 1 month) or until progression of disease during year 2 of follow up. Sera, whole blood and CBC with differential will be collected for immunoassays at initiation of immunotherapy, at initiation of degarelix, end of treatment visit and 10, 14 and 18 month (+/- 1 week). Patients will also have CT or MRI scans (chest, abdomen and pelvis) and bone scan at screening, end of treatment and 10 months after start of therapy. Toxicity evaluation will utilize CTCAE v5.0 criteria.

**Duration of Treatment:** Subjects will receive treatment for a total of 6 months or intolerable toxicity or side effects.

**Duration of Follow up:** Toxicity and laboratory tests will be graded using the NCI CTCAE v5.0 scoring system. Adverse events will be assessed continuously during the study and for 100 days after the last dose of treatment. In addition, patients will have PSA, serum testosterone checked every 2 months (+/- 1 week) or until progression of disease for year 1 of follow up and every 3 months (+/- 1 month) or until progression of disease for year 2 of follow up. Sera, PMBCs and CBC with differential will be collected for immunoassays collected at end of treatment visit and 10, 14 and 18 months following start of therapy. Patients will also need to have imaging done at end of treatment visit and 10 months after start of therapy. Subjects who are removed from the study for reasons other than progression of disease will be followed every 2 months to evaluate disease status and survival while the study remains open.

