# **STUDY OBJECTIVES**

## Primary Objective

- Determine the rate of PSA recurrence defined as a PSA >0.2ng/ml for radical prostatectomy patients or PSA >2.0ng/ml for patients who received other primary therapies (e.g. radiation, cryotherapy, brachytherapy) at a time point of 10 months after start of therapy.
- Determine the safety and tolerability of either nivolumab or nivolumab plus BMS-986253 in combination with degarelix in men with hormone-sensitive prostate cancer.

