#### STATISTICAL CONSIDERATIONS

#### Study Design and Sample Size

This is a multicenter, 2-arm phase 1b/2 trial to evaluate the activity of Nivolumab or Nivolumab plus BMS-986253 with IADT using Degarelix in men with hormone sensitive prostate cancer with a rising PSA. The primary endpoints of this trial is rate of PSA recurrence 10 months after start of therapy. Within the context of this proposed trial, we will target a decrease in post-therapy PSA recurrence at 10 months of 25% compared to a historical recurrence rate of 50% with intermittent ADT alone. Probabilities of type I and type II error will be set at 0.05 and 0.2 respectively. The study will include a total of 23 evaluable patients per arm. This study design yields at least 80% power to detect a PSA recurrence rate of 25% at 10 months after start of therapy (compared to the null hypothesis of 50%) at a significance level of 5%. Accounting for a dropout rate of 20%, we will plan to enroll a total of 30 patients per arm.

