#### Study Endpoints

We will use one-sided binomial tests to compare the post-therapy PSA recurrence rate in each arm with the historical recurrence rate of 50%. To compare the secondary outcomes between the two arms, Kaplan-Meier estimators and log-rank tests will be used to compare time-to-event variables (e.g., time to PSA recurrence, time to recovery of testosterone, and time to next anti-cancer treatment); Chi-squared tests will be used to compare incidence rates (e.g., incidence of metastases); t-tests will be used to compare continuous measurements (e.g., changes immune cell density and proximity). We will set the nominal significance level at 5%. Only patients undergoing randomization to the treatment arms will be used for comparison between the treatment arms.

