#### Analysis Populations

## Intention-to-treat population

All patients who meet eligibility criteria and receive at least one dose of the study drug will be included in the analysis of the primary and secondary endpoints, even if there are subsequent protocol deviations.

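### The primary endpoint is scored on the month-10 PSA alone, so a man whose PSA is held down by non-protocol therapy can count as recurrence-free

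*Combined protocol and SAP*

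**What the plan says.** Primary Objective gives the event purely as a PSA threshold: "Determine the rate of PSA recurrence defined as a PSA >0.2ng/ml for radical prostatectomy patients or PSA >2.0ng/ml for patients who received other primary therapies". General Design gives the assessment: "The primary endpoint will be evaluated by assessing the PSA 10 months after start of therapy". The statistical section repeats it: "The primary endpoints of this trial is rate of PSA recurrence 10 months after start of therapy". None of the three mentions therapy outside the protocol.

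The intention-to-treat population, used for the primary and secondary endpoints, is every eligible man with at least one dose, "even if there are subsequent protocol deviations". Number of Subjects and Study Design and Sample Size instead count 23 evaluable patients per arm, with 30 enrolled to allow for 20% dropout. The available text does not define evaluable.

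Other therapy appears only under Study Endpoints, where "time to next anti-cancer treatment" is a time-to-event outcome compared between arms. On men who leave, the Duration of Follow up paragraph says: "Subjects who are removed from the study for reasons other than progression of disease will be followed every 2 months to evaluate disease status". It adds survival, but names neither PSA nor new therapy.

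**The concern.** The Introduction sets the aim: a longer interval free of androgen deprivation therapy (ADT), with the disease controlled. It also says that ADT controls disease rapidly. A man who stops for toxicity or by choice and then restarts ADT outside the study would therefore be expected to have a low PSA at month 10. Scored on PSA alone, he counts in favour of the strategy he left. He need not have had an earlier PSA recurrence, so a rule that catches early recurrences would not catch him.

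Each arm is tested against a fixed 50% in a small sample, where one or two reclassified men can change the result. The trial is open-label and the plan does not say how to score these men. The choice between recurrence-free, failure and exclusion could therefore be made with the outcome in view.

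**Working it through.** **Inputs.** Null recurrence 50%, target 25%, type I error 0.05, type II error 0.2, 23 evaluable and 30 enrolled per arm, 20% dropout (Study Design and Sample Size). One-sided binomial test in each arm (Study Endpoints). The number m of men who start other therapy and have a suppressed month-10 PSA is not in the documents; m = 1 to 4 is assumed.

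**Step 1: reproduce the design.** The cutoff c is the largest value with P(X ≤ c | n, 0.50) ≤ 0.05.

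- n = 23: c = 7, exact type I error 0.0466, power P(X ≤ 7 | 23, 0.25) = 0.8037. This agrees with "This study design yields at least 80% power to detect a PSA recurrence rate of 25% at 10 months after start of therapy".
- n = 30: c = 10, exact type I error 0.0494, power 0.8943.
- Dropout: 23 / (1 − 0.20) = 28.75, so 29; the plan enrols 30.

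**Step 2: three ways to score the m men.** The remaining n − m men recur at 50% (for type I error) or 25% (for power).

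- Recurrence-free: type I error = P(Y ≤ c | n − m, 0.50).
- Failure: P(Y ≤ c − m | n − m, p), with p = 0.50 or 0.25.
- Excluded: the exact test is redone on n − m men with its own cutoff.

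n = 23:

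| m | Recurrence-free: type I | Failure: type I / power | Excluded: type I / power |
|---|---|---|---|
| 0 | 4.7% | 4.7% / 80.4% | 4.7% / 80.4% |
| 1 | 6.7% | 2.6% / 69.9% | 2.6% / 69.9% |
| 2 | 9.5% | 1.3% / 56.7% | 3.9% / 74.4% |
| 3 | 13.2% | 0.6% / 41.5% | 2.1% / 61.7% |
| 4 | 18.0% | 0.2% / 26.3% | 3.2% / 66.8% |

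n = 30:

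| m | Recurrence-free: type I | Failure: type I / power | Excluded: type I / power |
|---|---|---|---|
| 0 | 4.9% | 4.9% / 89.4% | 4.9% / 89.4% |
| 1 | 6.8% | 3.1% / 83.4% | 3.1% / 83.4% |
| 2 | 9.2% | 1.8% / 75.0% | 4.4% / 86.2% |
| 3 | 12.4% | 1.0% / 64.3% | 2.6% / 78.6% |
| 4 | 16.3% | 0.5% / 51.5% | 3.8% / 82.0% |

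**Step 3: one data set, different conclusions.** Take 23 men with m = 2 and 7 recurrences among the other 21. Scored as recurrence-free, the count is 7 of 23 and the arm passes (cutoff 7). Scored as failures, it is 9 of 23 and the arm does not pass. Excluded, it is 7 of 21 and the arm does not pass (cutoff 6).

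**The case against.** A reader might infer that the plan scores these men as successes. No section says so. That result needs a PSA obtained at month 10, a value below threshold, and a place in the denominator. Follow-up after removal covers disease status and survival without naming PSA, and the evaluable count with its dropout allowance leaves exclusion possible. It is also not certain that therapy begun after leaving the study is a protocol deviation. These points limit the claim to what the literal rule allows. They also show that the plan supports more than one scoring.

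A reader might extend the point to a man with a new lesion at the end-of-treatment scan who switches therapy while his PSA is low. The documents do not support this well. PSA checks run until progression, and the follow-up of removed men is for those removed for other reasons. He is more likely to have no month-10 PSA than a favourable one.

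Nor do the documents show that such men will be frequent. Treatment lasts 6 months, which leaves about 4 months to month 10, and listing time to next treatment as an outcome does not show that it will occur that early. A man who would have stayed below threshold anyway adds no bias. The calculation allows for this, since each switcher would otherwise recur with probability 50%.

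Two more points stand. Counting these men as failures is one of several defensible strategies, and it costs power. General Design also refers to a Section 12 that is not in the available text, so a rule there cannot be ruled out.

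**Conclusion.** The concern holds in a limited form. Followed literally, the PSA-only endpoint and the intention-to-treat population allow a man whose PSA is suppressed by non-protocol therapy to count as recurrence-free, which runs against the trial's stated aim. The undefined evaluable set leaves room to exclude him instead.

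Under the assumption that every such man has a suppressed month-10 PSA and is kept in the analysis, a single one takes the type I error above the planned 5% (6.7% with 23 men, 6.8% with 30). Four take it to 18.0% and 16.3%. These figures show how sensitive the test is. They do not predict the trial's actual error rate, because the number of such men is unknown. A claim that the result is certainly biased, or biased more in one arm, would go beyond the documents.

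The exposed period also depends on the assessment date. The Introduction places the primary endpoint 12 months after completion of therapy, whereas Primary Objective, General Design and the statistical section place it 10 months after start. These must be reconciled.

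**What to change.** - In Primary Objective, General Design, and Study Design and Sample Size, state that starting any non-protocol prostate-cancer therapy before the month-10 PSA counts as a primary-endpoint failure, whatever the PSA value.
- Prespecify two sensitivity analyses: excluding such men, and the PSA-only result.
- Define evaluable and reconcile it with the intention-to-treat population.
- Apply a matching rule to relapse-free survival (Secondary Objectives) and time to PSA recurrence (Study Endpoints).
- Report the number of such men by arm and reason.
- Check whether the benchmark, "compared to a historical recurrence rate of 50% with intermittent ADT alone", treated new therapy in a comparable way. If it did not, a change in this trial's definition alone would make the comparison unlike.

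The change is one of wording. The start date of other therapy should already be collected, because time to next treatment is a planned outcome, although the available text does not show the data collection. The real cost is a higher observed recurrence rate and lower power if such men occur. With 23 men, power falls from 80% to 70% with one and 57% with two; with 30 men, from 89% to 83% and 75%. This is an analysis definition only and does not affect when other therapy may be given.

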#### Number of Subjects

The study will include a total of approximately 30 patients per arm to achieve at least 23 evaluable patients per arm. This study design yields at least 80% power to detect a PSA recurrence rate of 25% at 10 months after start of therapy (compared to the null hypothesis of 50%) at a significance level of 5%. Accounting for a dropout rate of 20%, we will plan to enroll a total of 30 patients per arm.

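### The stated 80% power holds at exactly 23 evaluable patients per arm, but not at 24, 25 or 27, although Number of Subjects attaches it to 23 or more

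*Combined protocol and SAP*

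**What the plan says.** Number of Subjects gives the target as a minimum: "The study will include a total of approximately 30 patients per arm to achieve at least 23 evaluable patients per arm". The next sentence makes the power claim: "This study design yields at least 80% power to detect a PSA recurrence rate of 25% at 10 months after start of therapy", against a null of 50% at a 5% significance level.

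Study Design and Sample Size repeats the power claim but gives a single number: "The study will include a total of 23 evaluable patients per arm". It also fixes the error rates: "Probabilities of type I and type II error will be set at 0.05 and 0.2 respectively". Both sections reach the enrolment figure in the same way: "Accounting for a dropout rate of 20%, we will plan to enroll a total of 30 patients per arm".

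Study Endpoints names the test: "We will use one-sided binomial tests to compare the post-therapy PSA recurrence rate in each arm", each compared with the historical 50%. It does not say that the test is exact. The supplied text prints no success cutoff (largest number of recurrences that counts as success) for any sample size.

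The Intention-to-treat population section says that eligible patients who "receive at least one dose of the study drug will be included in the analysis of the primary and secondary endpoints".

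**The concern.** A power statement attached to a minimum sample size reads as a guarantee: reach 23 and the power is 80% or better, and extra patients can only help. For a binomial test on small numbers that is not so. The success cutoff is a whole number. When one more patient is added and the cutoff does not move, the test becomes stricter and power falls.

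What is at stake is the accuracy of the printed power over the range of numbers the trial may deliver. A secondary issue is that the cutoff changes with the number analysed, so it is best printed before the data are seen.

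**Working it through.** **Inputs.** Null recurrence rate 0.50 and one-sided binomial test in each arm (Study Endpoints). Alternative rate 0.25 and a minimum of 23 evaluable (Number of Subjects). Type I error 0.05, type II error 0.2 and 23 evaluable (Study Design and Sample Size). Enrolment of 30 per arm and 20% dropout (both sample-size sections).

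**Formulas.** Let X be the number of recurrences among n patients.
- Cutoff: k(n) = the largest k with P(X ≤ k | n, 0.50) ≤ 0.05.
- Power: P(X ≤ k(n) | n, 0.25).

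**Reproducing the plan's figure at n = 23.** P(X ≤ 7 | 23, 0.50) = 0.0466 and P(X ≤ 8 | 23, 0.50) = 0.105, so the cutoff is 7. Power = P(X ≤ 7 | 23, 0.25) = 0.8037. Type II error = 1 − 0.8037 = 0.1963, inside the planned 0.2. The one-sided normal-approximation formula also leads to 23: [(1.645 × 0.5 + 0.842 × √(0.25 × 0.75)) / 0.25]² ≈ 22.5, rounded up to 23. The plan's figure is confirmed.

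**The same calculation from 23 to 30.**

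| n | Success if recurrences ≤ | Exact type I error | Exact power at 25% |
|---|---|---|---|
| 23 | 7 | 4.66% | 80.4% |
| 24 | 7 | 3.20% | 76.6% |
| 25 | 7 | 2.16% | 72.7% |
| 26 | 8 | 3.78% | 82.0% |
| 27 | 8 | 2.61% | 78.6% |
| 28 | 9 | 4.36% | 86.2% |
| 29 | 9 | 3.07% | 83.4% |
| 30 | 10 | 4.94% | 89.4% |

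At 24, 25 and 27 the next cutoff up is not available, because its type I error would be 7.58%, 5.39% and 6.10%. The shortfalls against 80% are 80 − 76.6 = 3.4 points at 24, 80 − 72.7 = 7.3 at 25 and 80 − 78.6 = 1.4 at 27.

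**Which n the plan implies.** 30 × 0.8 = 24. The plan does not print this number. It may have worked upward instead: 23 / 0.8 = 28.75, rounded to 30.

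**Would a normal-approximation test remove the dips?** Its cutoff is the largest whole number not above n/2 − 1.645 × √n/2.
- n = 24: 12 − 4.03 = 7.97, so 7. The cutoff and power are unchanged at 76.6%.
- n = 25: 12.5 − 4.11 = 8.39, so 8. Power is 85.1%, but the true type I error is 5.39%.
- n = 27: 13.5 − 4.27 = 9.23, so 9. Power is 88.7%, but the true type I error is 6.10%.

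So it does nothing at 24, and at 25 and 27 it reaches 80% only by exceeding the stated 5%.

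**The case against.** The strongest reply is that nothing was miscalculated. Study Design and Sample Size names 23 without qualification, and its figure is right there. On this view the minimum in Number of Subjects is a recruitment floor, and the power sentence describes the design at its planned number. That reading is possible, and it is why the statistical section needs no correction. But the sentence in Number of Subjects follows directly on a minimum, and a reader will take it to cover larger numbers too.

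Second, the dips come from discreteness. Where power drops, the attained type I error drops with it, so protection against a false positive is never weakened. This stands in full.

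Third, the number analysed may not be 24. If the population of all eligible dosed patients is used and 28 to 30 are analysed, power is 83.4% to 89.4%. This also stands. The supplied text does not say how the evaluable number relates to that population, so any row of the table could apply.

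Fourth, a binomial test is ordinarily understood to be exact, in which case the 5% level and n together fix the cutoff. That is the natural reading, so a printed table is a safeguard and not a missing decision rule. It would still remove any argument over a result such as 8 recurrences in 25, where the exact p-value is 0.054 and the normal approximation gives z = (8 − 12.5)/2.5 = −1.8 and p = 0.036.

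A reader might go further and infer that 23 per arm is too few, that the trial is underpowered overall, or that its type I error is inflated. The documents support none of these. The claim is met at 23 and at four of the seven larger numbers up to 30, and the exact test stays within 5% at all of them.

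**Conclusion.** The power claim in Number of Subjects is wrong as written for three of the eight numbers from 23 to 30: 24, 25 and 27. One of these is the number implied by the plan's own enrolment and dropout. The claim is right at 23, so the corresponding statement in Study Design and Sample Size stands.

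The size is minor: 3.4, 7.3 and 1.4 percentage points. The result assumes an exact one-sided binomial test held at or below 5% and a true recurrence rate of exactly 25%. The importance of 24 rests on multiplying 30 by 0.8, which the plan does not itself do. This is an inaccurate statement that should be corrected; it gives no reason to change the design.

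**What to change.** 1. In Number of Subjects, limit the claim to 23: exact power is 80.4% at 23 evaluable patients per arm. Add that it ranges from about 73% to 89% over 23 to 30, and is 76.6% at 24.
2. In Study Endpoints, say that the one-sided binomial test is exact, and print the success cutoff for each number: 7 recurrences or fewer at 23 to 25, 8 at 26 and 27, 9 at 28 and 29, and 10 at 30. The table above can be used as it stands.
3. Leave the figure at 23 in Study Design and Sample Size, the 30 enrolled per arm and the choice of test unchanged.

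The cost is a sentence or two of wording and an eight-row table, with no extra patients. The printed power becomes less favourable at 24, 25 and 27 and more favourable at 26 and at 28 to 30.
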